WCM	Weill Cornell Medicine

Protocol Summary

Please provide a brief protocol summary.

Full Title:	Mobile Cognitive Behavior Therapy Targeting Anxiety Disorders
Short Title:	Mobile CBT in Anxiety
Clinical Phase:	N/A – no drug or device involved
Principal Investigator:	[name]
Sample Size:	N = 120
Accrual Ceiling:	We plan to screen up to 300 subjects.
Study Population:	18-25 year olds who have been diagnosed with an anxiety disorder as per the Anxiety Disorders Interview Schedule.
Accrual Period:	We anticipate complete accrual of participants taking up to 1 year
Study Design:	Participants in this study will use an online Cognitive Behavior Therapy program to assist with treatment of their anxiety symptoms. This program is being developed by Weill Cornell Medicine faculty as part of the University of Pennsylvania Center for Health Incentives and Behavioral Economics's established online platform called "Way to Health." All participants in the study will be using the program; as this is a pilot study testing the feasibility of using an online CBT program plus non-monetary incentives. Participants will be told to use the program for at least 20 minutes per day, 2 days per week, for up to 6 weeks. Participants will check in once a week in person or over the phone or a HIPAA-compliant virtual meeting platform. There will also be one follow up visit 6 weeks after they have stopped using the program.
Study Duration:	3 months
Study Agent/	
Intervention Description:	There is no drug or invasive device being used; rather, we are simply providing an online Cognitive Behavior Therapy program through an existing online platform called "Way to Health"
Primary Objective:	The primary objective is to examine different ways of motivating people to make use of the online therapy program, and to assess whether social supports are as efficacious, or more efficacious, than a reward mechanism such as non-monetary incentives. We will randomize subjects to one of three conditions: a social support condition, a gain-framed condition in which participants can earn "points" for completing their assigned sessions, and a

loss-framed condition in which participants lose “points” for failing to complete their assigned sessions on time. We will compare change in anxiety from baseline to end of treatment between these three conditions.

Secondary Objectives: A secondary objective will be to evaluate whether the three incentive conditions are associated with different levels of treatment engagement. We will measure the amount of time participants use the program and administer a questionnaire to assess participants’ subjective impressions of the program. We will compare these measures across the three incentive conditions.

Exploratory Objectives: We will collect neuroimaging data from a subset of participants who choose to participate in MRI scans and/or electroencephalographic (EEG) recordings pre-intervention and post-intervention. We will examine these scans for neural changes pre-to post-intervention. We will also assess associations between symptom improvement and time spent on different modules within the program.

Endpoints: We will administer several questionnaires that will assess severity of symptoms of anxiety in order to assess the efficacy of the program over time.

SCHEMA

All study assessments will be conducted either in person, over the phone, or on a HIPAA-compliant virtual meeting platform. Decisions about how to conduct visits will be made with participants, depending on safety and convenience.

[figure not shown]

Table of Contents

1. STUDY OBJECTIVES	6
1.1 Primary Objectives.....	6
1.2 Secondary Objectives	6
1.3 Exploratory Objectives.....	7
2. BACKGROUND	7
2.1 Disease	7
2.2 Investigational Agent or Device	7
2.3 Rationale.....	8
2.4 Risk/Benefit Assessment.....	9
3. SUBJECT SELECTION	9
3.1 Study Population	9
3.2 Inclusion Criteria.....	9
3.3 Exclusion Criteria.....	9
4. REGISTRATION PROCEDURES	10
4.1 Patient Registration.....	10
5. STUDY PROCEDURES	10
5.1 Schedule of Evaluations	10
5.1.1 Screening Visit	10
5.1.2 Treatment Phase	10
5.2 Treatment Administration	13
5.3 General Concomitant Medication and Supportive Care Guidelines.....	14
5.4 Duration of Therapy and Criteria for Removal from Study	14
5.5 Duration of Follow Up.....	14
6. DOSING DELAYS/DOSE MODIFICATIONS	14
7. PHARMACEUTICAL INFORMATION.....	14
8. CORRELATIVE/SPECIAL STUDIES.....	14
9. MEASUREMENT OF EFFECT	15
10. DATA REPORTING / REGULATORY CONSIDERATIONS.....	15
10.1 Data Collection	15
10.1.1 REDCap	15
10.2 Regulatory Considerations	16
11. STATISTICAL CONSIDERATIONS	16

11.1 Study Design/Endpoints	16
11.2 Sample Size/Accrual Rate	17
11.3 Stratification Factors	17
11.4 Analysis of Endpoints	17
11.4.1 Analysis of Primary Endpoints	17
11.4.2 Analysis of Secondary Endpoints	17
11.5 Interim Analysis.....	18

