1.1 Primary Objectives

We plan to develop an online cognitive behavioral therapy program, in collaboration with the Center for Health Incentives and Behavioral Economics (Wharton School) that can be integrated into their online platform, Way to Health (<https://www.waytohealth.org>) that has been developed over the past 10 years and automates many of the research functions necessary for conducting randomized controlled trials of behavior interventions and strategic telehealth programs in areas related to primary care medicine. The platform is an efficient, scalable, and low cost way to test behavioral interventions. To date, the platform has supported NIH-funded interventions that focus on medication adherence; weight loss; monitoring of blood sugar, blood pressure and weight; physical activity; smoking cessation; sleep and patient compliance.

One of the key features of the online platform (Way to Health) is its capacity to embed various incentive tools such as gamification and social support to the CBT intervention. In this context, these incentive components are novel to the delivery of any CBT treatment. A main hypothesis to be tested in this objective is whether the social support component will have a particular advantage to increase efficacy of CBT in this age group. This social support component will potentially extend the benefits of a group therapy approach, including connection with others, support, and encouragement. To test this hypothesis, we will randomize participants to one of three incentive structure conditions: a gain-framed incentive in which participants earn points for completing sessions, a loss-framed incentive in which they lose points for failing to complete sessions, and a social support incentive in which participants can identify a person they know to receive updates about their progress and support them throughout their time in the program. Participants will not be required to choose a person they know to receive updates about their use of the program; instead, they can choose to have a member of the study team serve as their social support if they are assigned to this condition.

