5.1.2.4 Visit 4 (+7 days from Visit 3): Midpoint

Protocol # 1803019086
Version Date 12/27/2022

- Rumination Response Scale (RRS)
- Hamilton Rating Scale for Depression (HAM-D)
- Hamilton Rating Scale for Anxiety (HAM-A)

- Generalized Anxiety Disorder 7-item Scale (GAD-7)
- Patient Health Questionnaire 9 (PHQ-9)
- The Temporal Experience of Pleasure Scale (TEPS)
- Positive and Negative Affect Schedule (PANAS)
- Emotion Regulation Questionnaire (ERQ)
- Multidimensional Experiential Avoidance Questionnaire (MEAQ)
- Pittsburgh Sleep Quality Index (PSQI)
- World Health Organization Quality of Life short-form scale (WHOQOL-BREF)
- Life Events Scale for Students (LESS)
- Anxiety Sensitivity Index (ASI-3)
- Liebowitz Social Anxiety Scale (LSAS)
- Sensitivity to Punishment and Sensitivity to Reward Questionnaire (SPSRQ)
- Mobile Application Rating Scale: user version (uMARS)
- Digital Working Alliance Inventory (D-WAI)
- Medication Tracking

- Check in about how the app is working.

5.1.2. 5 Visit 5 (+7 days from Visit 4)

- Generalized Anxiety Disorder 7-item Scale (GAD-7)
- Patient Health Questionnaire 9 (PHQ-9)
- Medication Tracking
- Check in about how the app is working.

5.1.2. 6 Visit 6 (+7 days from Visit 5)

- Generalized Anxiety Disorder 7-item Scale (GAD-7)
- Patient Health Questionnaire 9 (PHQ-9)
- Medication Tracking
- Check in about how the app is working.

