5.2 Treatment Administration

Treatment will be administered on an *outpatient* basis.

Participants will be asked to engage with the mobile application at least 2 days a week

Protocol # 1803019086

Version Date 12/27/2022

for 20-25 minutes per session. These sessions can be done at the participants' convenience for various lengths of time. These tasks can be boring or frustrating for

some people, but participants are allowed to take breaks, or to make sessions shorter. Participants may also decide to stop participating at any time.

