10.2 Regulatory Considerations

All protocol amendments and consent form modifications will be made by the Principal Investigator.

11. Statistical Considerations

As this study is a pilot to determine feasibility of the CBT mobile application including non-monetary incentives, we do not anticipate high volume data. We intend to use the pilot data to submit an NIH grant where we will recruit a statistician to be a part of our research team.

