11.1 Study Design/Endpoints

No subjects will be forced to end participation in the study based on a lack of engagement with the mobile CBT program. We will be looking at whether participants completed the protocol as intended (i.e. usage statistics across the 6 weeks). We will gather the qualitative data from participants when they come for the weekly check-in visits. We will analyze how often participants opened the mobile app, completed the exercises and whether they completed the 6 week protocol, and if not, at what time point they stopped participating. We have no set criteria regarding what percentage must finish the protocol; however, if less than 25% of participants complete the protocol as intended, we will re-evaluate our current procedures. Such information is a critical first step *before* testing the validity of the mobile CBT platform, which will be the scope of future proposals to the NIH. We will also be comparing differences in efficacy and treatment engagement between three different incentive conditions. We will not be comparing the mobile CBT to any other type of treatment at this initial stage.

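### The Summary's primary objective includes equal efficacy of social support, but the planned comparison of HAM-A change has no margin, so a non-significant difference could not support it

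*Combined protocol and SAP*

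**What the plan says.** The Protocol Summary, under Primary Objective, intends to "assess whether social supports are as efficacious, or more efficacious, than a reward mechanism such as non-monetary incentives", and then describes the analysis in one sentence: "We will compare change in anxiety from baseline to end of treatment between these three conditions". Section 1.1 states the main hypothesis in one direction only, namely "whether the social support component will have a particular advantage to increase efficacy of CBT in this age group". Section 11.1 adds "We will also be comparing differences in efficacy and treatment engagement between three different incentive conditions". Section 11.4.1 makes HAM-A the primary measure and compares its change from baseline to Visit 7 across the three conditions.

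No section gives a non-inferiority or equivalence margin, a rule based on a confidence interval, a significance level, a test or a named contrast.

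HAM-A is scheduled at baseline (5.1.2.1), at the Visit 4 midpoint (5.1.2.4) and at Visit 7 (5.1.2.7). Missing Visit 7 scores are foreseeable: 5.2 says "Participants may also decide to stop participating at any time", and 11.1 intends to record whether people completed the six weeks "and if not, at what time point they stopped participating". Section 11.4.1 does not mention baseline HAM-A as a covariate, the Visit 4 score, or participants who have no Visit 7 score.

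**The concern.** The Summary asks two questions, whether social support is better and whether it is as good. Section 1.1 and the analysis sections deal only with the first, or with differences in general. Concluding that one condition is as good as another needs a limit, fixed in advance, on how much worse it could be. Without one, failure to find a difference reflects the width of the interval as much as the truth.

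What is at stake is the conclusion the pilot may carry into the planned grant application. If social support were moderately worse than points, a non-significant result would still be likely, and the present Summary wording would leave room to report it as meeting the objective.

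A second, related matter is precision. A comparison of change that uses only baseline and Visit 7 can leave information unused that the schedule already collects, and may drop people who left after the midpoint.

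**Working it through.** **The plan's own figure.** The documents give no basis for 120 (no power, SD, expected difference or margin), so it cannot be reproduced. The accrual arithmetic holds: 300 / 12 = 25 per month.

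**Inputs.** From the documents: three arms (5.1.2.1), 120 expected to complete (11.2), HAM-A change as the primary measure (11.4.1). Assumed: equal allocation, so 120 / 3 = 40 per arm with a Visit 7 score; two-sided 5%; no multiplicity adjustment; differences in units of the SD of HAM-A change. The Summary speaks of a single reward mechanism and the documents name no contrast, so both readings are shown: social support against one points arm (40 v 40) and against the two points arms pooled (40 v 80).

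**Step 1: interval half-width.** Half-width = t(0.975, 117) × SE, with t = 1.980.
- Pairwise: SE = √(1/40 + 1/40) = 0.2236 SD; half-width 0.443 SD.
- Pooled: SE = √(1/40 + 1/80) = 0.1936 SD; half-width 0.383 SD.

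At an assumed SD of 5 to 8 HAM-A points, that is about 2.2 to 3.5 points pairwise and 1.9 to 3.1 points pooled.

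**Step 2: how often a true deficit is non-significant.** Noncentral t with noncentrality = deficit / SE (df 78 pairwise, 118 pooled).

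| True deficit | Pairwise, change score | Pooled, change score | Pairwise, baseline-adjusted (ρ = 0.5) |
|---|---|---|---|
| 0.2 SD | 86% | 82% | 82% |
| 0.3 SD | 74% | 66% | 67% |
| 0.4 SD | 58% | 47% | 47% |
| 0.5 SD | 40% | 27% | 28% |

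The last two columns nearly agree because 0.75 × 2/40 = 0.0375 = 1/40 + 1/80.

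**Step 3: what an equal-efficacy claim would need.** For non-inferiority, one-sided 2.5%, arms truly equal, 40 v 40, the smallest margin with 80% power is 0.63 SD. Adjusted for baseline at ρ = 0.5 it is 0.55 SD.

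**Step 4: gain from baseline adjustment.** Let HAM-A have the same variance σ² at baseline and Visit 7, with correlation ρ. A change score has variance 2σ²(1 − ρ). Visit 7 adjusted for baseline has residual variance σ²(1 − ρ²). The ratio is (1 − ρ²) / [2(1 − ρ)] = (1 + ρ)/2, which is 0.65, 0.75 or 0.85 at assumed ρ of 0.3, 0.5 or 0.7.

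**Step 5: gain from Visit 4.** With complete data it adds nothing to the Visit 7 comparison. If a fraction d is lost after the midpoint, the variance relative to a completers-only baseline-adjusted analysis is about 1 − R²d, where R² is the squared partial correlation of Visit 4 with Visit 7 given baseline. Assumed correlations of 0.6 (baseline–Visit 4), 0.7 (Visit 4–Visit 7) and 0.5 (baseline–Visit 7) give R² = (0.7 − 0.6 × 0.5)² / [(1 − 0.36)(1 − 0.25)] = 0.16 / 0.48 = 0.333. For d of 10%, 20% or 30% the variance falls by about 3%, 7% or 10%.

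**The case against.** Section 11 opens "As this study is a pilot to determine feasibility of the CBT mobile application including non-monetary incentives", and 11.1 leaves testing the platform's validity to later proposals. Limited precision is expected of a pilot, and nothing here asks for more participants. That stands, and it keeps the severity modest. It does not remove the mismatch, because 11.4.1 itself makes the comparison of anxiety change the primary purpose.

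Four stronger readings are tempting, and the documents do not support them.
- A reader might infer that the trial sets out to demonstrate equivalence. The Summary says only that it will assess the question, and the documents never use the terms equivalence or non-inferiority. The clause may be loose summary language.
- A reader might infer that a null result will be reported as equality. No section says so. The wording merely leaves room for it.
- A reader might infer that the plan has chosen an inefficient change-score test. Section 11.4.1 names no test. Comparing change is also compatible with a baseline-adjusted or mixed model, and if one was intended, the Step 4 gain is already in hand.
- A reader might infer that deficits up to about 0.4 SD would be missed more often than not. That holds for the pairwise change-score test (58%), but not with the points arms pooled or with baseline adjustment (47% each).

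**Conclusion.** The concern holds in a limited form. The Summary's equal-efficacy clause is out of line with 1.1 and has no analysis that could answer it, so a non-significant difference could not support it. This conclusion rests on the text alone. The size rests on assumptions: with 40 per arm and change scores, the interval extends about 0.44 SD (pairwise) or 0.38 SD (pooled) either side of the estimate, and a true 0.3 SD deficit goes undetected about 74% or 66% of the time.

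The bare description in 11.4.1 can be improved with data already scheduled. The variance reduction to 0.65 to 0.85 is relative to a plain change-score analysis with equal variances. The Visit 4 contribution is small and arises only where people leave after the midpoint. For a feasibility pilot this is worth correcting, but it is not a serious flaw.

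**What to change.** 1. In the Summary, drop the equal-efficacy clause so that the objective matches 1.1, or reword the aim as estimating the differences between conditions. Add: *Differences between conditions are reported with 95% confidence intervals; a non-significant difference will not be read as equal efficacy.*

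2. In 11.4.1, replace the bare comparison with: *HAM-A at Visit 7 is compared between arms in all randomised participants, with baseline HAM-A as covariate, in a repeated-measures model that includes the Visit 4 HAM-A.*

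Both are wording changes and need no new visits, data or participants. The first gives up the equal-efficacy claim; keeping it would require a justified HAM-A margin set in advance, and Step 3 shows how wide that margin would have to be at this size. The second has a small downside: the model assumes that loss is explained by the observed HAM-A scores. Which contrast to use (each points arm, the two pooled, or an overall test) is a separate trade-off that these changes do not settle.

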1.1 Primary Objectives

We plan to develop an online cognitive behavioral therapy program, in collaboration with the Center for Health Incentives and Behavioral Economics (Wharton School) that can be integrated into their online platform, Way to Health (<https://www.waytohealth.org>) that has been developed over the past 10 years and automates many of the research functions necessary for conducting randomized controlled trials of behavior interventions and strategic telehealth programs in areas related to primary care medicine. The platform is an efficient, scalable, and low cost way to test behavioral interventions. To date, the platform has supported NIH-funded interventions that focus on medication adherence; weight loss; monitoring of blood sugar, blood pressure and weight; physical activity; smoking cessation; sleep and patient compliance.

One of the key features of the online platform (Way to Health) is its capacity to embed various incentive tools such as gamification and social support to the CBT intervention. In this context, these incentive components are novel to the delivery of any CBT treatment. A main hypothesis to be tested in this objective is whether the social support component will have a particular advantage to increase efficacy of CBT in this age group. This social support component will potentially extend the benefits of a group therapy approach, including connection with others, support, and encouragement. To test this hypothesis, we will randomize participants to one of three incentive structure conditions: a gain-framed incentive in which participants earn points for completing sessions, a loss-framed incentive in which they lose points for failing to complete sessions, and a social support incentive in which participants can identify a person they know to receive updates about their progress and support them throughout their time in the program. Participants will not be required to choose a person they know to receive updates about their use of the program; instead, they can choose to have a member of the study team serve as their social support if they are assigned to this condition.

1.2 Secondary Objectives

In addition to assessing efficacy of the three incentive strategies, a secondary objective is to evaluate the extent to which each strategy enhances engagement with the CBT intervention. Necessary to the real-world success of any technology-based health intervention is the frequency with which the user interacts with the technology and the user's perception of how helpful and easy to use it is; even the most well-designed treatment will not help anyone if people never use it. We hypothesize that the social support incentive strategy may increase use and enjoyment of the program. We will use both objective data collected by the online CBT program and subjective ratings reported by

study participants to evaluate differences in engagement between the gain-framed, loss-framed, and social incentive conditions.

1.3 Exploratory Objectives

We will collect neuroimaging data from a subset of participants who choose to participate in MRI scans and/or electroencephalographic (EEG) recordings pre-intervention and post-intervention. We will examine these scans for neural changes along with examining questionnaires and interviews to assess changes in symptoms pre- and post-intervention. We will also assess associations between symptom improvement and time spent on different modules within the program.

2. Background

2.1 Disease

The disease being researched is anxiety disorder, a category of psychiatric disorders that includes phobias, social anxiety, and panic disorders. It is characterized by stress that is disproportionate to the potential consequence of an event, an inability to stop worrying, and general restlessness. It has a one-year prevalence of 10.6% and a lifetime prevalence of 16.6%. In addition, it has seen a rise in prevalence in younger populations in recent years (Remes, 2016).

2.2 Investigational Agent or Device

The online CBT program will be developed with the consultation of a behavioral economics researcher at the University of Pennsylvania's Wharton School (Center for Health Incentives and Behavioral Economics; <https://chibe.upenn.edu>). The program will be integrated into their established online platform (Way to Health; <https://www.waytohealth.org>) that includes various incentive tools. Our program will include modules addressing, among others: psychoeducation, emotion monitoring tools, cognitive restructuring strategies, mindfulness practices, exposure hierarchy building and maintenance tools, an evolving list of weekly exposure goals, exposure exercise processing tool, and as-needed motivational enhancement and relapse prevention modules. Module content will be continually updated based on ongoing patient assessment. For example, the exposure hierarchy will be an interactive tool with evolving fear and avoidance ratings based on weekly exposure exercises accomplished and anxiety data collected. These data will then inform recommendations for weekly exposure tasks, including when to repeat exposures and when to move on to a more challenging task. The online CBT platform will include an interactive dashboard to provide the user with their program "stats" based on patient goals will be entered into the system; it will provide prescribed outcome measures for tracking progress toward

Protocol # 1803019086

Version Date 12/27/2022

goals. Participants will be told that they must engage with the online CBT platform for at

least 20-25 minutes per day, 2 days per week. They are allowed to use the program more frequently than this if they want to.

Although the proposed version of this app is new, the content and its structure are similar to how Cognitive Behavioral Therapy (CBT) is commonly delivered. We have a collaboration with University of Pennsylvania's Wharton School (Center for Health Incentives and Behavioral Economics; <https://chibe.upenn.edu>), who have an established online platform called Way to Health. Way to Health has been used to deliver interventions to thousands of patients. In 2017, the platform supported 38 research projects and 11 clinical pilots. We are working closely with [name]., Ph.D. at University of Pennsylvania who has demonstrated how incentives can increase adherence to mobile interventions for weight loss, physical activity, safe driving, smoking cessation, among others (e.g. Patel, Volpp & Asch, 2018, NEJM; Patel et al., 2017, JAMA; Volpp et al., JAMA Internal Med). The productive team at Way to Health allows for quick development while maintaining a high level of rigor. All of our timeline goals as we have developed this project have been met by the University of Pennsylvania team so we are confident that we will have timely delivery of the mobile application.

